**Study Protocol and Statistical Analysis Plan**

**Document Date: July 25, 2018**

**Uploaded: August 22, 2018**

# Obstructive Sleep Apnea and Cardiac Electrophysiologic Biomarkers of Sudden Cardiac Death

## BACKGROUND

Ventricular tachyarrhythmias (VTA) are a major cause of sudden cardiac death which account for half of cardiac mortality affecting approximately 3 million individuals world-wide. In fact, rates of sudden cardiac death are in excess of the mortality accompanying breast, lung and colorectal cancer *combined*. Data suggest that 50-85% of sudden cardiac deaths are attributable to ventricular tachycardia or ventricular fibrillation. Obstructive sleep apnea (OSA), an entity characterized by repetitive episodic breathing cessation during sleep, represents a highly prevalent physiologic stressor afflicting upwards of 17% of the population. Emerging experimental data implicate OSA-related intermittent hypoxia, autonomic nervous system fluctuations and alterations in intrathoracic pressure on risk of cardiac arrhythmogenesis (**Figure 1, Appendix**). Similarly, data from epidemiologic studies—much of which has been generated by our group— support a strong association of OSA and ventricular tachyarrhythmias (VTA). Accordingly, clinic-based studies show nocturnal predilection to increased sudden cardiac death in OSA compared to those without OSA. In stark contrast to other etiologies of cardiac mortality, the incidence of sudden cardiac death has only marginally reduced over the last decade. *Although, based upon compelling experimental mechanistic data and epidemiologic data, OSA represents a potential novel therapeutic target to reduce VTA-induced sudden cardiac death; this key area of investigation remains vastly understudied.* OSA has been associated with cardiac repolarization abnormalities and implicated in sudden cardiac death. A biologically plausible mechanism by which OSA exerts this lethality is by QT interval prolongation, a known marker of VTA leading to cardiac death. Congenital long QT syndrome (LQTS) is a familial arrhythmogenic disorder characterized by prolonged QT interval on the electrocardiogram and increased propensity for VTA. Preliminary data identify an association of the extent of severity of OSA and progressive prolongation of the corrected QT interval in LQTS.

***We propose a study to serve as an initial step to overcome existing critical knowledge gaps, i.e. characterizing the influence of OSA on QT prolongation in LQTS as well as other more common clinical scenarios such as in acquired heart disease and arrhythmogenic drugs. Furthermore, given the complete lack of data on treatment effect, we plan to examine the impact of OSA treatment on QT prolongation and innovative T wave morphologic characteristics via an interventional study. Expected results will be of high impact given ability to generate pilot data which can serve as the foundation to be used to identify and inform future screening and treatment approaches for management and/or mitigation of VTA propensity. Data will also set the stage to identify key outcomes for OSA clinical trials in these vulnerable populations. Our team is uniquely poised to carry out the proposed research as we have assembled a team with clinical and research expertise in sleep disorders and cardiac electrophysiology with experience conducting clinical trials, epidemiologic studies and cardiac electrophysiologic signal processing and an already partially assembled cohort of patients with prolonged QT interval.***

## SPECIFIC AIMS

**Aim 1.** To examine the extent that OSA severity and degree of hypoxia are associated with QT interval prolongation and novel T wave morphologic assessments on serial hourly 12-lead ECG collected during overnight polysomnography and also corrected QT interval (QTc) from daytime 12-lead ECG in those predisposed to prolonged QT interval, i.e. those with 1) LQTS, 2) acquired heart disease and 3) arrhythmogenic drugs.

**Hypothesis 1.** We hypothesize that the extent of severity of OSA and degree of hypoxia (defined by the apnea hypopnea index and percentage of sleep time spent <90% respectively) will be associated

with QT interval prolongation and novel T wave morphologic assessments even after consideration of confounding factors including age, sex, race and body mass index. Exploratory analyses will examine the mediation of cardiac substrate (left ventricular ejection fraction) on these associations.

**Aim 2.** To investigate the effect of OSA treatment with 3-month continuous positive airway pressure (CPAP) on QT interval duration as well as novel biomarkers of T wave morphology observed on ECG data collected during overnight polysomnography and also QTc collected from daytime 12-lead ECG in those with LQTS.

**Hypothesis 2.** We postulate that 3-month treatment of OSA will reduce the QT interval and improve novel electrophysiologic markers of ventricular stability in patients who are vulnerable to VTA and sudden cardiac death.

## **SIGNIFICANCE**

The application addresses an area of high significance, i.e. elucidation of OSA as a novel, biologically plausible therapeutic target to mitigate VTA and sudden cardiac death. This is an important area of investigation given the substantial contribution VTA confers to sudden cardiac death and unchanged incidence of sudden cardiac death over the last decade underscoring the need to identify novel preventative targets. Data generated from the proposal will set the stage to advance scientific understanding of the impact of OSA as an exacerbating factor of cardiac electrophysiologic markers of lethality with the potential to inform public health policy to reduce sudden cardiac death. Results will lay the foundation to provide preliminary data to inform personalized medicine approaches and risk stratification to focus efforts on identification of OSA in those with QT prolongation and therefore vulnerable to VTA.

## **INNOVATION**

The innovation of the proposal is multi-faceted including evaluation of not only standard QT interval indices, but also cutting edge signal processing to examine cardiac electrophysiologic biomarkers predictive of lethal VTA. These innovative QT morphologic indices will also be examined in relation to OSA and hypoxia as likely physiologic triggers—an area that has yet to be investigated. Moreover, although there are scant clinical research data which support an association of OSA and QT prolongation, the impact of reversal of OSA pathophysiology with CPAP has yet to be investigated. The data culminating from our efforts will allow for generation of critical data to lay the foundation for clinical trials and extramural NIH R01 level funding.

## **PRELIMINARY DATA/FEASIBILITY**

### ***Epidemiologic Work from our Group Supporting Strong Magnitude of Association of Obstructive Sleep Apnea and Ventricular Tachyarrhythmia***

Our group has generated data from an epidemiologic perspective which has demonstrated a strong association of OSA and ventricular cardiac arrhythmia. Specifically, population-based our work conducted in the Sleep Heart Health Study (n~600) and the Outcomes of Sleep Disorders in Older Men study (n~3K) support a strong association of OSA and nocturnal ventricular arrhythmia, i.e. complex ventricular ectopy and nonsustained ventricular tachycardia (NSVT), even after adjustment for confounding influences of underlying cardiovascular risk and obesity (**Figures 2-4, Appendix**). These findings translate to an impressive approximate 2-fold increased risk of ventricular arrhythmia in those with moderate to severe OSA. Moreover, utilizing a case crossover design, i.e. a design which is best used with a transient exposure and outcome, we have shown immediate temporal relationships of discrete apnea and hypopnea events and episodes of NSVT namely an 18-fold higher odds of NSVT in those periods of apnea or hypopnea compared to those without.

## ***Experience Examining Cardiac Electrophysiological Indices and Obstructive Sleep Apnea***

We identified a statistically significant association of polysomnogram (PSG)-based heart rate variability (HRV) autonomic function biomarkers and incident AF over and 8.0 ± 2.6 year follow up period and these associations were modified by measures of sleep disordered breathing in 2350 participants of a multi-center prospective study (Outcomes of Sleep Disorders in Older Men Study). Specifically, we observed that a lower LF/HF and lower LF were associated with higher AF incidence (LF/HF Q1 vs. Q4: 1.46, 1.02-2.08, LF Q1 vs. Q4: 1.46, 1.02-2.10) and that the highest PAC quartile had a 3-fold increased AF risk (2.99, 1.94-4.62) compared to the lowest quartile. A significant interaction of obstructive apnea was observed in the LF-AF relationship (0.045) (**Figures 5, Appendix**). These findings indicated that sleep-related reduced sympathovagal balance (LF/HF) and increased atrial ectopy are independently associated with future AF; a relationship modified by obstructive apnea.

## ***Clinical Trial Experience/Recruitment and Retention***

Our group has conducted several clinical trials and interventional studies utilizing CPAP involving collaboration with sleep medicine and cardiologists/electrophysiologists for which we have either met or exceeded recruitment goals and have had expected retention (drop out range: 10-20%). (*NIH/NHLBI HL079114: Oxidative Stress in Sleep Apnea and Cardiac Disease, NHLBI 1RC2HL101417: Phase II Trial of Sleep Apnea Treatment to Reduce Cardiovascular Morbidity, NHLBI R01 HL 109493: Elucidation of the Risk of Sleep Apnea in Atrial Fibrillation*).

## **METHODS**

### ***Participant Eligibility Criteria and Process for Recruitment***

We plan to recruit 50 patients with QT prolongation as identified by ICD 10 426.82 from the Cleveland Clinic. At the Cleveland Clinic, we will utilize the Knowledge Program query tool and EResearch along with [name] Registry: Cleveland Clinic internal registry for inherited arrhythmias (IRB: 16-1094) platforms to identify potential recruits. Those patients with congenital LQTS or QT prolongation related to acquired heart disease or arrhythmogenic drugs will be eligible. Approximately ~500 patients/year (42/month) with QT prolongation are evaluated at the Cleveland Clinic. Assuming 50% meet eligibility criteria and 50% of those are interested then ~n=125 patients will be recruited/year (n=16/month over 8 months). This translates into n~150 potential participants over the 8-month recruitment period which exceeds the n=50 cases required to meet sample size requirements.

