## **PROTOCOL**

Potential participants will come to the Cleveland Clinic Clinical Research Unit (CRU) for informed consent, eligible participants will undergo a 12 lead electrocardiogram. If the participants is found to have long QT syndrome ( $QT_c \geq 450$  in men and  $\geq 470$  in women) they will continue on in the study. If they are found to not have long QT syndrome they will exit the study. If continuing on in the study the participant will undergo a fasting venipuncture and blood pressure measurements. The participant will then be shown how to use the portable sleep study hook-up and continuous 12-lead ECG monitoring to be monitored in the home setting. The sleep study and ECG monitors will be returned by a courier service the next morning.

Those participants who are identified to have OSA (apnea hypopnea index  $\geq 5$ , estimate 50% of those recruited) on the portable sleep monitoring will be invited to wear CPAP for 2-3 months with a follow up visit with repeat portable polysomnographic and continuous electrophysiologic assessments and CRU visit for bloodwork and blood pressure.

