#### **Alternative/Pitfalls**

1. Although we have experience with successful cross-institutional collaboration and recruitment, it is possible that recruitment efforts may not be successful with the approach as outlined via EResearch and the KP query tool. If this is the case, we will plan to pre-screen patients in electrophysiology clinics.
2. We will not have research-grade time-concordant echocardiography to assess as a covariate factor, however, it is anticipated that many of the patients will have clinical ECHO studies for which we will conduct data extraction.
3. Although there will be heterogeneity in the sample in terms of the etiology of QT prolongation, this will be a strength as albeit we will be somewhat limited in power, we will be able to examine subgroup effect sizes.

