#### **Timeline**

Please refer to **Figure 7** for the timeline. The first 2-4 weeks will be dedicated to solidifying protocols, establishing database and personnel training. Recruitment will begin month 1 until month 8 (goal recruitment 7-8 participants per month) with collection of in-tandem sleep monitoring and continuous 12-lead ECG monitoring with blood work. In months 9-12 statistical analyses will be conducted with

preparation of abstracts (submitted to Heart Rhythm and American Thoracic Society meetings) as well as manuscripts entitled “*Association of Obstructive Sleep Apnea and Corrected QT interval and Novel T Wave Morphologic Characteristics*” and “*Impact of Continuous Positive Airway Pressure on Corrected QT interval and Novel T Wave Morphologic Characteristics*” and preparation of an R01 application.

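### Does the recruitment projection of 16 a month and about 150 in 8 months, which its own inputs do not support, call for a change to the plan?

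*Combined protocol and SAP*

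**What the plan says.** The section Participant Eligibility Criteria and Process for Recruitment sets a target of 50 patients and supports it with a short calculation. The starting flow is "Approximately ~500 patients/year (42/month) with QT prolongation are evaluated at the Cleveland Clinic". Half are assumed eligible and half of those interested, and the paragraph continues "then ~n=125 patients will be recruited/year (n=16/month over 8 months". It then concludes: "This translates into n~150 potential participants over the 8-month recruitment period which exceeds the n=50 cases".

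Four other places bear on the point:

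- The Timeline section has recruitment running from month 1 to month 8, with "goal recruitment 7-8 participants per month".
- The PROTOCOL section has a 12-lead ECG after consent, with a QTc threshold by sex. Of those below it, the plan says "If they are found to not have long QT syndrome they will exit the study".
- The recruitment section also names a "Cleveland Clinic internal registry for inherited arrhythmias" as a source, and the background mentions "an already partially assembled cohort of patients with prolonged QT interval". Neither is given a size.
- Alternative/Pitfalls allows for slow recruitment through the database tools: "If this is the case, we will plan to pre-screen patients in electrophysiology clinics".

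**The concern.** This is the plan's only calculated support for reaching 50 patients in 8 months, and two of its figures fail a hand check. The annual flow is correctly divided by 12 to give 42 a month, yet the annual yield of 125 is turned into a monthly figure that would use it all up in 8 months. The 8-month total is then larger than the yearly total it is said to come from.

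A reader who accepts about 150 would think the study could lose two of every three candidates and still reach 50. If the true supply is nearer 83, it can lose only about two of every five. That could matter here because some consented patients leave at the ECG check. Had the sample size, recruitment goal or timetable rested on the larger figures, the slip would have affected the conduct of the study.

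**Working it through.** **Inputs.** From the recruitment section: 500 patients a year (42 a month), 50% eligible, 50% of those interested, 50 required. From the Timeline: 8 months of recruitment, goal 7-8 a month. From Clinical Trial Experience/Recruitment and Retention: drop-out of 10-20% in the group's earlier studies.

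**The plan's figures that reproduce.**

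- Monthly flow: 500 / 12 = 41.7, stated as 42.
- Yearly yield: 500 × 0.5 × 0.5 = 125, as stated.

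**The figures that do not.**

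- Monthly yield: 125 / 12 = 10.4. From the plan's own monthly flow, 42 × 0.25 = 10.5. The plan states 16. Dividing 125 by 8 gives 15.6, so a full year's yield was probably placed in 8 months; that origin is an inference.
- Yield over 8 months: 10.42 × 8 = 83.3 (or 10.5 × 8 = 84). The plan states about 150. Its own 16 a month gives 16 × 8 = 128.

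**Can 150 be recovered another way?**

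| Reading | Result |
|---|---|
| 8 months of flow, both 50% factors | 83-84 |
| 9 months of flow, both factors | 94 |
| 12 months of flow, both factors | 125 |
| 16 a month for 8 months | 128 |
| 8 months of flow, one 50% factor (42 × 8 × 0.5) | 168 |
| 8 months of flow, no factor (42 × 8) | 336 |

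None gives 150. Reaching it in 8 months would take 150 / 8 = 18.75 a month, or a yield of 150 / (500 × 8 / 12) = 45% in place of 25%.

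**Size of the slip.** 150 / 83.3 = 1.80, an overstatement of about 80%. Supply over requirement is 83.3 / 50 = 1.67, against 150 / 50 = 3.0. The surplus is about 33, against 100. These comparisons take 150 to count the same kind of person as 83.

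**Does anything downstream move?**

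- Rate needed for 50: 50 / 8 = 6.25 a month. The corrected 10.4 exceeds it and reaches 50 in 50 / 10.42 = 4.8 months.
- Timeline goal: 7 × 8 = 56 to 8 × 8 = 64. The corrected 83 exceeds both.
- If 50 had to be completers at 10-20% drop-out: 50 / 0.9 = 55.6, so 56; 50 / 0.8 = 62.5, so 63. The corrected 83 exceeds both.
- Power: both statements under POWER BY AIM start from n=50. Neither uses 16 or 150.

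**The ECG check.** The documents do not say whether the 50% eligible share already includes the QTc threshold. If it does, 83 stands. If it does not, reaching 50 from this flow alone needs a pass rate of at least 50 / 83.3 = 60%; under the stated 150 it would be 50 / 150 = 33%. No pass rate is given.

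**The case for a change.** The strongest case for a change is that the margin is the whole purpose of the paragraph. An overstatement of 80% is too large to pass as rounding, and the smaller margin matters more because patients can leave after consent at the ECG check. The correction would take one sentence and cost nothing.

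Much of this stands. The figures are wrong on the stated inputs, and approximate signs do not excuse them. The more generous readings do not rescue them either. Database searches might reach a full year's patients inside 8 months, since the paragraph counts patients evaluated and not only new ones, but that yields 125 and the plan does not claim it. The registry and the existing cohort might add patients, but they have no stated size and are not part of the sum. The term potential participants might mean a wider pool than recruits, but the pool before the interest step is about 168.

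The step from a wrong figure to a needed change does not stand. The recruitment target in use is the Timeline's 7-8 a month, which the corrected rate exceeds. The open question about the ECG pass rate is separate: it exists with either figure, and replacing 150 by 83 would not answer it. If recruitment is slow, the plan already has clinic pre-screening as its response.

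**Conclusion.** The arithmetic complaint is correct: the stated inputs give about 10 a month and about 83 over 8 months, not 16 and about 150, and the two stated figures also disagree with each other (128 against 150). It is a clerical slip with no consequence for the trial. The sample size, power statements, analyses, timetable and recruitment goal do not use either figure, and 83 exceeds 50, the 56-64 implied by the Timeline, and the 56-63 that would allow for 10-20% drop-out.

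This rests on the plan's own 500 a year and its two 50% shares, and on the eligible share covering the QTc check. If that check removes further patients, the stated flow still supplies 50 provided at least 60% pass. Any contribution from the registry or existing cohort would add to the supply, by an amount the documents do not give. A reader judging feasibility should use a ratio of about 1.7 rather than 3. Rewriting the sentence would change nothing the study does or can conclude.

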#### *Inclusion Criteria:*

1) Clinical diagnosis of QT prolongation as described above, 2) Age 18-75 years, 3) Individuals able to participate in at least 2 overnight sleep and physiologic assessments over a 3 month period.

*Exclusion Criteria:* 1) Use of specific OSA treatments (CPAP, oral appliances), 2) Use of supplemental oxygen, 3) Severe chronic insomnia, 4) Circadian rhythm disorder (e.g. shift work sleep disorder, delayed or advanced sleep phase syndrome), 5) Insufficient sleep syndrome defined by reported sleep duration < 4 hrs, 4) Unstable medical conditions (e.g., new onset or changing angina, a myocardial infarction or congestive heart failure exacerbation documented within the previous 3 months, uncontrolled hypertension (BP>170/110), uncontrolled diabetes mellitus (HbA1c>9.0), uncontrolled hypo- or hyperthyroidism), 5) Psychiatric disorders which are inadequately treated, 6) Compromised competence, 7) Alcohol abuse (currently drinks >5 alcoholic drinks/day), 8) Inability to provide informed consent, 9) Illicit drug use over last 6 months. *Rationale for criteria:* Patients with sleep disorders will be excluded as other sleep disorders may influence arrhythmogenesis. Those on treatment for SDB will be excluded because treatment would preclude assessment of OSA pathophysiologic effects on QT biomarkers.

Those with unstable medical conditions or rapid or uncontrolled heart rate will be excluded due to safety reasons.

## **PROTOCOL**

Potential participants will come to the Cleveland Clinic Clinical Research Unit (CRU) for informed consent, eligible participants will undergo a 12 lead electrocardiogram. If the participants is found to have long QT syndrome ( $QT_c \geq 450$  in men and  $\geq 470$  in women) they will continue on in the study. If they are found to not have long QT syndrome they will exit the study. If continuing on in the study the participant will undergo a fasting venipuncture and blood pressure measurements. The participant will then be shown how to use the portable sleep study hook-up and continuous 12-lead ECG monitoring to be monitored in the home setting. The sleep study and ECG monitors will be returned by a courier service the next morning.

Those participants who are identified to have OSA (apnea hypopnea index  $\geq 5$ , estimate 50% of those recruited) on the portable sleep monitoring will be invited to wear CPAP for 2-3 months with a follow up visit with repeat portable polysomnographic and continuous electrophysiologic assessments and CRU visit for bloodwork and blood pressure.

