**Aim 2. Examine the effect of OSA (AHI $\geq$ 5) treatment for 3 months on QT interval duration.**

For this subgroup of OSA (AHI $\geq$ 5, estimated to be 50% of n=50) and we will perform t-tests to compare pre- and post- treatment mean outcome (Primary outcome: QT duration) and also novel quantitated T wave morphologic measures. For either outcome for which a departure in normality is found (based on the Shapiro-Wilk test) but a transformation of the outcome can not be found to adequately address the issue, we will use the Wilcoxon signed rank sum test to detect a difference in the distribution of the pre- and post- responses. This assessment is not intended to be confirmatory, but rather to provide estimates of variability and effect sizes to inform future studies/randomized trials. Linear regression models will then be developed to QT interval duration at the 3-month visit by conditioning on baseline QT interval duration, baseline OSA, and time from baseline to 3-month visit. Additional adjusted models will carefully consider the covariates list above.

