#### **POWER BY AIM.**

**Specific Aim 1.** A sample size of 50 will be able to detect 0.59 standard deviations with 80% power (and 0.62 with 90% power), assuming a 2-sided alpha level of 0.05 which is sufficient for generation of pilot data.

**Specific Aim 2.** Using a two-sample t-test (2-sided 0.05 alpha-level) to test for a difference in mean variation between the SDB (AHI $\geq$ 5) and no SDB groups, a sample size of 50 (25 with OSA and 25 without OSA) will detect mean differences within 0.46 standard deviations with 80% power and 0.53 standard deviations with 90% power.

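### The Aim 2 power statement is for an OSA versus no-OSA two-sample test, but the plan analyses only a pre/post change within OSA and schedules no second recording for anyone else

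*Combined protocol and SAP*

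**What the plan says.** Three sections bear on this.

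- **Schedule (PROTOCOL).** Everyone who passes the QTc entry check has one home sleep study with 12-lead ECG. Those with AHI of 5 or more, estimated at half of those recruited, "will be invited to wear CPAP for 2-3 months with a follow up visit with repeat portable polysomnographic and continuous electrophysiologic assessments". Nothing further is described for AHI <5.
- **Analysis (Analytic Method by Aim, Aim 2).** The text opens "For this subgroup of OSA" and compares outcomes before and after treatment with t-tests, with the Wilcoxon signed rank test as fallback. It then regresses 3-month QT on baseline QT, baseline OSA and time between visits. It states that the assessment is not confirmatory and is meant to supply variability and effect sizes for later trials.
- **Power (POWER BY AIM, Specific Aim 2).** "Using a two-sample t-test (2-sided 0.05 alpha-level") is used "to test for a difference in mean variation between the SDB" and no-SDB groups, and "a sample size of 50 (25 with OSA and 25 without OSA) will detect mean differences within 0.46 standard deviations with 80% power", with "0.53 standard deviations with 90% power". The quantity called *mean variation* is not defined anywhere.

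The Inclusion Criteria also admit "Individuals able to participate in at least 2 overnight sleep and physiologic assessments over a 3 month period". The Clinical Trial Experience section reports dropout of 10–20% in the group's earlier studies; the power section does not apply it.

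**The concern.** The power statement should describe the test that will be run. Here the test differs (two-sample against paired), the population differs (OSA and no OSA against OSA alone), and the endpoint is undefined. Under an aim about 3 months of CPAP, the natural reading of *mean variation* is change over follow-up, and the schedule gives half the sample no second value from which to compute one.

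Two things are at stake. A reader would take 0.46 SD as the sensitivity of the Aim 2 analysis when it is not. A reader would also expect Aim 2 to deliver a between-group result, and so some control for change over time, when the analysis is a single-group pre/post change. That matters because entry depends on exceeding a QTc cut, Future Directions looks to the study for the effect size of OSA treatment, and the Timeline plans a paper on the impact of CPAP.

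**Working it through.** **Inputs.** N = 50, half with OSA, so 25 and 25 (PROTOCOL; POWER BY AIM). Two-sided alpha 0.05; stated detectable differences 0.46 SD at 80% and 0.53 SD at 90% power (POWER BY AIM). Dropout 10–20% (Clinical Trial Experience). The documents give no SD for QTc and no correlation between visits.

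**Step 1. Who can be scored for change.** With OSA: 0.50 × 50 = 25 with a scheduled second recording. Without OSA: 0. A two-sample test of change would be 25 versus 0. The paired test keeps its planned 25 pairs if all who are invited accept and return.

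**Step 2. Reproducing the stated figures.** For a two-sample t-test, noncentrality = d / √(1/n₁ + 1/n₂) with n₁ + n₂ − 2 degrees of freedom. At 25 versus 25, √(2/25) = 0.283.

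- Normal approximation: (1.960 + 0.842) × 0.283 = 0.79 SD (80%); (1.960 + 1.282) × 0.283 = 0.92 SD (90%).
- Exact noncentral t: 0.81 SD and 0.94 SD.
- Exact power at the stated values: 36% at 0.46 SD and 45% at 0.53 SD.

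The stated pair is not reproduced. Other readings, in SD units of the quantity tested:

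| Design | 80% power | 90% power |
|---|---|---|
| 25 vs 25, one-sided | 0.71 | 0.84 |
| 50 vs 50 | 0.57 | 0.65 |
| 75 vs 75 | 0.46 | 0.53 |
| 25 pairs | 0.58 | 0.68 |
| 50 pairs | 0.40 | 0.47 |

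Only 75 per group (N = 150) matches in this table. The figures could also be change expressed in SDs of a single QT measurement, where the SD of change is √(2(1 − r)). For 25 versus 25 this needs r of about 0.84: 0.81 × √0.32 = 0.46 and 0.94 × √0.32 = 0.53. For 25 pairs it needs r of about 0.69: 0.584 × √0.62 = 0.46. The documents state neither correlation. For 25 versus 25, r from 0.3 to 0.8 gives 0.96 down to 0.51 SD at 80% power.

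**Step 3. Power for the planned test.** Paired t-test: noncentrality = d√n with n − 1 degrees of freedom, d in SDs of the paired change.

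| Pairs | 80% power | 90% power |
|---|---|---|
| 25 | 0.58 | 0.68 |
| 22 (25 × 0.9 = 22.5, rounded down) | 0.63 | 0.73 |
| 20 (25 × 0.8) | 0.66 | 0.76 |

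On this scale, 25 pairs have 60% power at 0.46 SD and 72% at 0.53 SD. The 95% CI half-width is t₂₄/√25 = 2.064/5 = 0.41 SD of the paired change.

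**Step 4. What a single-group change may contain.** This step is illustrative; the correlations and the cut are assumed. Suppose the outcome is the ECG used for entry, entry cuts a normal distribution at its mean, and test-retest correlation is r. The expected fall without any treatment effect is (1 − r) × 0.798 SD, and the SD of change among those admitted is √(0.363(1 − r)² + 1 − r²).

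- r = 0.7: 0.239 / 0.737 = 0.32 SD of the change.
- r = 0.9: 0.080 / 0.440 = 0.18 SD of the change.

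The fall would be smaller for an overnight recording separate from the entry ECG.

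**The case against.** The best defence is that the Aim 2 analysis is coherent as it stands. It is a pre/post comparison in treated OSA participants, expressly not confirmatory, and needs no follow-up in AHI <5. The OSA versus no-OSA contrast appears only in the power sentence, and *mean variation* might mean a baseline level or within-night variation, which the first recording gives for everyone. All of this stands, and it rules out saying that Aim 2 cannot be analysed. It does not rescue the power statement: on the baseline reading the comparison is an OSA association, which is Aim 1's question, and it is still not the Aim 2 test.

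Three stronger readings are tempting and are not supported.

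- **That inclusion criterion 3 conflicts with the schedule.** It asks whether people are able to complete two assessments. It is applied before AHI is known, and anyone enrolled may turn out to have OSA. It promises no second visit to all, so no edit is needed.
- **That AHI <5 participants must be recorded twice.** This would yield a non-randomised contrast of treated OSA with untreated no-OSA participants, so it would not isolate a CPAP effect. It would remove only drift common to both groups; if QT differs by OSA status, as Hypothesis 1 predicts, one entry cut need not produce equal regression to the mean. The size of any drift is assumed, not documented. The Continuous Overnight 12-lead ECG Monitoring section has a coordinator apply the sensors at a visit, so the price is up to about 25 further visits as well as recordings.
- **That a randomised control exists.** The CPAP section refers to participants randomised to CPAP, but no allocation procedure or control arm is described.

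**Conclusion.** The point holds as a mismatch between the Aim 2 power statement and both the Aim 2 analysis and the schedule. The stated 0.46 and 0.53 SD describe a test the plan does not run and do not follow from 25 versus 25 (0.81 and 0.94 SD of the quantity tested). If *mean variation* is change, the comparison has about 25 versus 0 participants.

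The paired test that is planned detects 0.58 SD of the paired change at 80% power and 0.68 SD at 90% with 25 pairs, and about 0.63–0.66 and 0.73–0.76 SD with 22 to 20 pairs. This assumes that half of 50 have OSA, that changes are roughly normal, and that uptake of CPAP and return for follow-up leave the pairs shown.

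The resulting estimate is an uncontrolled change that may include regression to the mean after the QTc entry cut. The documents do not allow its size to be fixed. The pilot analysis itself remains feasible.

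**What to change.** 1. **POWER BY AIM, Specific Aim 2.** Delete the OSA versus no-OSA two-sample comparison with its 0.46 and 0.53 SD. Replace it with, for example: *With 25 OSA participants recorded before and after treatment, a two-sided 0.05 paired t-test has 80% power for a mean change of 0.58 SD of the paired difference and 90% power for 0.68 SD; with 22 to 20 pairs after 10–20% dropout the values are about 0.63–0.66 and 0.73–0.76 SD.*
2. **Analytic Method, Aim 2.** State that the result is an uncontrolled pre/post change, reported with a 95% CI, which may include regression to the mean after the QTc entry cut and is not an isolated CPAP effect. Use the same description in the planned paper.

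The cost is wording only: no participant, visit or assay is added. The downside is that the stated detectable difference becomes less favourable than 0.46/0.53 SD.

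Optional: if the sponsor does want an OSA versus no-OSA comparison, it should define the endpoint. If that is change, a second recording in AHI <5 participants would be needed, and 25 versus 25 would detect 0.81 SD of change at 80% power and 0.94 SD at 90%. That is a resource decision, not a required correction.
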